
In order to maintain participant confidentiality and also maintain blindedness of the research interviewers, JVS case-files will be kept separate from research assessment records and linked by an identifying code, with code access limited to study investigators. Research records will be kept in locked file cabinets in locked staff offices at JVS and at The University of Michigan. No part of the research record collected for this project, will be released without written consent from the participant. These procedures will very likely be effective in preventing threats to confidentiality.

D 6. POTENTIAL BENEFITS OF THE PROPOSED RESEARCH TO THE PARTICIPANT AND OTHERS

The risk/benefit ratio in this research is very good. Benefits include free psycho-education and treatment, potential enhancement of compliance and treatment response associated with extensive professional attention provided in repeated and detailed assessments, and contribution to science and to the future treatment of unemployed adults with SocAD. Risks include temporary anxiety increases, and the possibility of non-improvement of SocAD-specific symptoms, especially for those participants assigned to the VAU control condition. In sum, risks are temporary and minor to moderate, whereas benefits are many and apply to all research participants. We believe this risk/benefit ratio is very reasonable for each participant given the extensive professional evaluation, symptom improvements, destigmatization, monetary compensation, and therapeutic support resulting from study participation.

D 8. DATA SAFETY AND MONITORING PLAN

This plan specifies our proposed study's oversight and monitoring procedures. These will be put in place to ensure the safety of study participants as well as the validity and integrity of our data. The plan was developed based on guidance from the NIH Notice for Data and Safety Monitoring (OD-00-038).

Participants recruited for the proposed study are 18-60 year-old unemployed adults with social anxiety disorder. We have included several safety and monitoring components in this plan.

1. Institutional Review Board Approval. Approval for the proposed research study, including informed consent documents, is approved at Institutional Review Board for Human Participant Research at the University of Michigan Medical School (IRB) and pending at the UCLA IRB. We plan to secure "continuing approval" for the project yearly and to notify the IRB of any adverse events that occur. This notification would occur promptly and in writing, in keeping with the policy of the IRB.

2. Project Staff Education on the Protection of Human Research Participants. All members of this study's research team have completed the required certification in good research and ethics practices as mandated by each University. Specifically, all UM research staff members and JVS Detroit staff members who will be leading WCBT groups have completed relevant, required modules of UM's online Program for Education and Evaluation in Responsible Research and Scholarship (PEERRS). All research staff will complete re-certification of PEERRS modules as required.

3. Data and Safety Monitoring Board. We will establish a Data Safety Monitoring Board (DSMB) to monitor human participant protections on an ongoing basis at the University of Michigan and at UCLA. The DSMB is a monitoring body established in keeping with NIH guidelines for the appropriate oversight and monitoring of the conduct of clinical trials. The DSMB will convene a minimum of two times each year, to review the following: (a) research protocol and plans for data and safety monitoring, (b) adverse events and unforeseen outcomes, (c) ethical issues related to recruitment activities, (d) risk management policies and activities, and (e) intermediary data analyses. They will evaluate the progress of the proposed intervention trial through regular assessments of data quality, participant recruitment, and risk versus benefit, retention, and performance of the trial site. The DSMB will make recommendations to the IRB and study investigators concerning continuation or conclusion of the trial.

Proposed members of the DSMB include University of Michigan faculty members [name] and [name] and UCLA faculty members Drs. [name] and [name], Department of Psychiatry and Biobehavioral Sciences. We will name an additional member from outside of the University to join each board. In keeping with the "NIH Policy for Data and Safety Monitoring," additional members will be included in the DSMB or consultants will be involved as necessary to interpret the data and ensure patient safety. For instance, the expertise of a biostatistician who is uninvolved with the study could potentially be needed.

Each year, the DSMB will issue a report that summarizes:

(1) All serious and unexpected adverse events (e.g., inpatient hospitalizations or significant worsening of clinical status) or other unanticipated problems that involve risk to study participants or others, and whether these appeared related to the study-based interventions or research assessment protocols.

(2) The committee's judgments regarding the assurance of the participants' safety, privacy, and confidentiality.

(3) Judgments as to whether research instruments have been administered appropriately while assuring participants' confidentiality.

(4) The committee's review of the study's progress toward recruitment goals, quality of data, treatment adherence, and participant retention/attrition rates.

(5) The committee's review of new research relevant to the safety of participants or the ethics of participation (for example, new therapeutic developments).

(6) Its recommendations as to whether risk/benefit ratios have changed to the extent that the trial should be modified or discontinued. Specific recommendations for protocol modifications will be described, with the accompanying rationale for each.

These yearly DSMB reports will be filed immediately with the IRB, as well as with the NIH Project Officer and the NIH Office for Human Research Protections (OHRP). The reports will include the dates that the committee met and the procedures used for monitoring participants' safety, confidentiality, and data integrity. The PI will take responsibility for reporting any serious and unexpected adverse events in a timely fashion directly to the DSMB and IRB. Actions taken by the IRB in response to adverse event reports will be immediately reported to the DSMB and the NIMH Project Officer and OHRP office. The PI's recognize the need for regular communication between the DSMB and the IRB.

The primary risk with the proposed study is suicide risk. We have developed a comprehensive protocol for responding to suicide risk. In every case, if a participant is determined to be at risk for suicide, several steps will be followed: (1) ongoing contact between the participant and group leaders at JVS will occur until risk is determined to be minimal; (2) Drs. [name] and [name] will be informed immediately and continuously apprised of any changes/developments in the participant's risk for suicide; (3) all assessments, conversations, and steps taken with the participant to ensure his or her safety will be thoroughly documented; (4) we will communicate with our IRB to determine the need for adverse event reporting, and any actions taken and outcomes will be reported to the IRB and the NIH.

All participants will be assessed for suicide risk using a modified version of the University of Michigan Hospital System suicide risk assessment protocol during their intake interview and at each subsequent major assessment point (baseline, post treatment, follow-up). If a participant is determined to be at risk based on responses to clinical assessment or routine weekly contact, the Research Associate or [name] will contact [name] immediately, by telephone or via paging system. [name] will then contact the participant immediately and further assess suicide risk. If risk is determined to be present, we will implement the following protocol for responding to suicide risk.

(1) Mild risk (e.g., suicidal ideation present without presence of current plan, low intent, presence of hope, no current means).

If the subject's suicidality is assessed in person:

- The individual participant will speak with [name]. At this meeting the participant will discuss the nature of their suicidal ideation/plan/intent and collaborate about a resolution.
- [name] will contact [name] via telephone.
- The individual participant will also be encouraged to discuss his or her feelings with their support networks (e.g., family, friends, service providers, etc.).
- Follow-up contact attempts will be provided by the research team until risk is determined to be minimal using contact strategies developed with the individual.
- Participants will be given a suicide wallet resource card.

If the subject's suicidality is assessed via telephone:

- The individual participant will speak with [name]. At this telephone meeting the participant will discuss the nature of their suicidal ideation/plan/intent and collaborate about a resolution.
- [name] will contact [name] via telephone.
- The individual participant will also be encouraged to discuss his or her feelings with their support networks (e.g., family, friends, service providers, etc.).
- Follow-up contact attempts will be provided by the research team until risk is determined to be minimal using contact strategies developed with the individual.
- The Detroit Wayne Authority Mental Health Access Center phone number will be shared with the client.

(2) Moderate risk (e.g., suicidal ideation present with additional risk factors: moderate intent, low hope, possible plan and/or possible means).

If the subject's suicidality is assessed in person:

- The individual participant will speak with [name]. At this meeting the participant will discuss the nature of their suicidal ideation/plan/intent to collaborate about a resolution.
- [name] will contact [name] via telephone or paging system.
- In collaboration with the client, the determination will be made whether or not the client will be transported to Detroit Receiving Hospital.
- The Detroit Wayne Mental Health Access Center phone number will be shared with the client via the suicide wallet card.
- The individual will also be encouraged to discuss his or her feelings with support networks (e.g., family, friends, service providers, etc.).
- If a support network is available and the participant refuses treatment, [name] will make contact with the support network person. If there is not a support network available, then a phone call will be initiated to the Detroit Wayne Authority Mental Health Access Center in the office with the goal of using this resource as a support system.
- A plan will be made for removing from the participant's dwelling any means with which to commit suicide, preferably with the assistance of family or trusted resources.

- Continuous follow-up phone contact (with [name], or [name]) ensuring the participant's safety will be made throughout the day and then on a daily basis until risk is determined to be mild. Phone calls will then occur less frequently until risk is determined to be minimal. The participant will be encouraged to return to JVS daily until risk is determined to be minimal. If he or she refuses, the client will be transported to Detroit Receiving Hospital.

If the subject's suicidality is assessed via telephone:

- The individual participant will speak with [name]. At this telephone meeting the participant will discuss the nature of their suicidal ideation/plan/intent to collaborate about a resolution.
- [name] will contact [name] via telephone.
- In collaboration with the client, the determination will be made whether or not the client will be transported to Detroit Receiving Hospital. Arrangements will be made with the local authorities to transport the client to Detroit Receiving Hospital.
- The individual will also be encouraged to discuss his or her feelings with support networks (e.g., family, friends, service providers, etc.).
- If a support network is available and the participant refuses treatment, [name] will make contact with the support network person. If there is not a support network available, then a 3-way phone call will be initiated to the Detroit Wayne Authority Mental Health Access Center with the goal of using this resource as a support system.
- A plan will be made for removing from the participant's dwelling any means with which to commit suicide, preferably with the assistance of family or trusted resources.
- Continuous follow-up phone contact (with [name] or [name]) ensuring the participant's safety will be made throughout the day and then on a daily basis until risk is determined to be mild. Phone calls will then occur less frequently until risk is determined to be minimal. The participant will be encouraged to return to JVS daily until risk is determined to be minimal. If he or she refuses, arrangements will be made with the local authorities to transport the client to Detroit Receiving Hospital.

(3) High risk (e.g., suicidal ideation present with several additional risk factors: high intent, no hope, a definite plan, and current means).

If the subject's suicidality is assessed in person:

- The individual participant will speak with [name]. At this meeting the participant will discuss the nature of their suicidal ideation/plan/intent to collaborate about a resolution.
- [name] will contact [name] via telephone or paging system.
- In collaboration with the client, a determination will be made whether or not the client will be transported to Detroit Receiving Hospital.
- If [name] or [name] determine that hospitalization is necessary, the participant will be sent via ambulance to Detroit Receiving Hospital. If the participant refuses to be taken to Detroit Receiving Hospital, the EMS personnel will be encouraged to call the Detroit Police for assistance.
- The Detroit Wayne Authority Mental Health Access Center phone number will be shared with the client via the suicide wallet card.
- The individual will also be encouraged to discuss his or her feelings with support networks (e.g., family, friends, service providers, etc.).
- If a support network is available and the participant refuses treatment, [name] will make contact with the support network person. If there is not a support network available, then a phone call will be initiated to Detroit Wayne Authority Access Center in the office with the goal of using this resource as a support system.
- A plan will be made for removing from their dwelling any means with which to commit suicide, preferably with the assistance of family or trusted resources.

- If the participant is not hospitalized, continuous follow-up phone contact (with [name] or [name]) ensuring the participant's safety will be made throughout the day and then on a daily basis until risk is determined to be mild. Phone calls will then occur less frequently until risk is determined to be minimal. The participant will be encouraged to return to JVS daily until risk is determined to be minimal. If he or she refuses, the client will be transported to Detroit Receiving Hospital.

If the subject's suicidality is assessed via telephone:

- The individual participant will speak via the telephone with [name]. At this telephone meeting the participant will discuss the nature of their suicidal ideation/plan/intent to collaborate about a resolution.
- [name] will contact [name] via telephone or paging system.
- In collaboration with the client, the determination will be made whether or not the client will be transported to Detroit Receiving Hospital. Arrangements will be made with the local authorities to transport the client to Detroit Receiving Hospital.
- The individual will also be encouraged to discuss his or her feelings with support networks (e.g., family, friends, service providers, etc.).
- If a support network is available and the participant refuses treatment, [name] will make contact with the support network person. If there is not a support network available, then a 3-way phone call will be initiated to the Detroit Wayne Authority Mental Health Access Center with the goal of using this resource as a support system.
- The clinician will remain in constant telephone contact until the participant's safety is ensured. Should the participant refuse hospitalization and it is deemed necessary, [name] will engage police and authorities in ensuring involuntary hospitalization.
- Any potential means with which to commit suicide will be removed from the dwelling, preferably with the assistance of family or trusted others.
- If the client is not hospitalized, continuous follow-up phone contact (with [name] or [name]) ensuring the participant's safety will be made throughout the day and then on a daily basis until risk is determined to be mild. Phone calls will then occur less frequently until risk is determined to be minimal. The participant will be encouraged to return to JVS daily until risk is determined to be minimal. If he or she refuses, arrangements will be made with the local authorities to transport the client to Detroit Receiving Hospital.

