If a consumer agrees to consider participating and a research associate is not present at JVS, the JVS professional will ask potential participants if they would like to fill out a contact form and have a Research Associate contact them at a later time. Contact form allows participants to provide phone number for themselves and another contact and an email address, Confidentiality will be emphasized. Research Associates will re-contact potential participants who voluntarily complete contact forms by phone and briefly describe the study. If participants contact research staff via the email provided on the contact form at any time during the study, research staff will respond via email. If the potential participant remains interested, the Research Associate will schedule an in-person meeting at JVS to obtain informed consent. Once informed consent is obtained, the participant will be offered an appointment for a baseline assessment interview. After completion of the baseline assessment interview, those who qualify to participate will be offered participation. .

Participants will be 300 men and women aged 18-60 who are seeking vocational services at JVS (96 JVSD; 204 JVSLA) who meet the inclusion and exclusion criteria below. We expect to be able to recruit enough JVS consumers to fill the groups within 3 to 4 weeks depending on potential participant flow. Our screening efforts have found that approximately 27% of JVS consumers score 5 or greater on the MINI-SPIN. Of those who

score 5 or more, we anticipate that approximately 70% will agree to undergo a formal baseline interview for the pilot study. Of these, we anticipate that approximately 83% will meet full study criteria. Of these, we anticipate that 75% will be randomized. We estimate that we will need to screen 2500 people over our 34-month recruitment interval (JVSD=850; JVSLA= 1650) in order to complete the RCT. Given the large number of new clients entering JVSD and JVSLA services each year, we do not anticipate any difficulty recruiting a *minimum* of 8 participants per month at JVSLA or 6 participants per month at JVSD, but we *expect* to recruit approximately 16 per month at JVSLA and 10 per month at JVSD, resulting in an average of 15 days waiting period or less before randomization.

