Inclusion. Participants will be JVS service-seeking adults who are unemployed, score at least five on the MINI-SPIN (Connor et al., 2001), meet structured interview criteria for SocAD. Participants taking psychotropic medications will be offered participation without restriction. We will monitor medication as a potential moderator of outcomes. Participants must agree to refrain from outside psychotherapy throughout the active 4-week treatment period.

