Group leader adherence and competency. Therapist competence and adherence in delivering WCBT will be measured by independent ratings of session audiotapes, using the Therapist Adherence Scale for CBT for SocAD (89) that we adapted to fit the WCBT manual (TAS-WCBT; see Appendix). Training of independent raters will involve didactic review of the WCBT manual and the TAS, followed by rating 8 sessions from one of the Phase 1 pilot groups in discussion with Drs. [name], [name] and [name]. This will be followed by an assessment of inter-rater reliability based on ratings of a second pilot group (8 sessions). During Phase 2, integrity of WCBT and group leader drift will be addressed by rating 3 randomly selected sessions of each WCBT group. Drs. [name], [name] and [name] will give feedback to group leaders as necessary. Our R34 project yielded impressive TAS-WCBT session fidelity ratings. Trained independent raters rated 23 of 56 WCBT sessions, on 1-to-5 scales, ranging from 1 (ineffective discussion) to 5 (extremely effective discussion). The average overall rating across sessions was 4.23 (SD=.66). We expect adherence and competence to be further enhanced via technology-assisted delivery of WCBT (computer-assisted CBT in the CALM study yielded good to excellent competencies and adherence) (61).

Diagnostic interviewer training & inter-rater reliability. Two independent evaluators (IE) at each site will be trained to complete interviews (MINI, BPRS, & MSIF – see Table 2). They will be trained by Drs. [name], [name] and [name] via a 3-day training course during which they will conduct 5 or more interviews until inter-rater agreement on ratings and diagnosis is satisfactory (80% agreement). Then, each IE will be observed doing five or more interviews until there is 90% agreement for the MINI and 95% for the BPRS and MSIF. Throughout the study, 25% of participants will be randomly selected to repeat their assessment battery at one randomly selected time-point by a different IE. Spearman correlation coefficients will be calculated between each rater with coefficients above 0.85 deemed acceptable. If this standard is not obtained, further training will be provided. Using these interviews, the IE's ratings will again be compared to consensus ratings obtained via discussion between that IE and the PI's/Co-I until the 0.85 criterion is met.

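### The ongoing rater check relies on a Spearman correlation above 0.85, which cannot detect a constant offset between raters on the BPRS and MSIF and sits badly with yes/no MINI diagnoses

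*Combined protocol and SAP*

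**What the plan says.** The section on diagnostic interviewer training and inter-rater reliability covers three instruments rated by two independent evaluators per site: the MINI, the BPRS and the MSIF. It uses two kinds of standard.

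- **Before the study.** Percent agreement: 80% in the training course, then observed interviews "until there is 90% agreement for the MINI and 95% for the BPRS and MSIF".
- **During the study.** Correlation: "25% of participants will be randomly selected to repeat their assessment battery at one randomly selected time-point by a different IE", after which "Spearman correlation coefficients will be calculated between each rater with coefficients above 0.85 deemed acceptable". A shortfall leads to further training and a comparison with "consensus ratings obtained via discussion between that IE and the PI's/Co-I until the 0.85 criterion is met".

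The section gives no ICC, kappa, mean-difference check or separate rule for diagnoses in the ongoing phase.

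The Cross Site Consistency Plan (Procedural consistency, items 2 and 3) adds yearly checks of adherence to assessment procedures, quarterly interviewer teleconferences, and blind cross-site rating of 5% of taped psychiatric diagnostic interviews. That last check uses rates of agreement and leads to retraining, but states no numerical threshold.

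**The concern.** An ongoing check exists to catch drift after certification. The only ongoing standard with a number attached measures whether two raters put cases in the same order, not whether they give the same scores. An evaluator whose BPRS or MSIF ratings move up or down uniformly keeps the same rank order and passes, both in the main check and in the comparison with consensus ratings.

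The MSIF is the protocol's measure of work productivity and performance, and each site has only two evaluators, so one drifting evaluator could affect a large share of a site's ratings. If different evaluators see the same participant at different visits, which the protocol does not rule out, an offset would also look like change over time.

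For the MINI the difficulty is of another kind. A correlation of present/absent ratings depends on prevalence, can be undefined, and may contradict the agreement level at which the evaluator was certified.

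**Working it through.** The 0.85 is a chosen threshold, so there is no derived figure to reproduce. The check is how that threshold behaves.

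**Inputs from the protocol.** Spearman above 0.85; certification at 90% (MINI) and 95% (BPRS, MSIF); 25% of participants re-interviewed; 300 participants, 96 in Detroit and 204 in Los Angeles. Expected pairs are 0.25 × 300 = 75, or 24 and 51 by site.

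**Assumptions, since the protocol gives no figures.** Underlying correlation between raters of .90; offsets from .25 to 1 SD; a range of prevalences. The 90% MINI figure is taken to apply to each diagnosis, which the protocol does not specify.

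**1. Rating scales.** With ratings of equal variance, correlation r and a constant offset of d SD, the two-way random-effects absolute-agreement ICC for a single rating is r / (1 + d²/2). Spearman does not involve d; simulation with r = .90 gives about .89 at every offset tried.

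| Offset d (SD) | Spearman | ICC = .9 / (1 + d²/2) |
|---|---|---|
| 0 | .89 | .90 |
| .25 | .89 | .9/1.031 = .87 |
| .5 | .89 | .9/1.125 = .80 |
| .75 | .89 | .9/1.281 = .70 |
| 1 | .89 | .9/1.5 = .60 |

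Setting .9 / (1 + d²/2) = .85 gives d² = 2 × (.9/.85 − 1) = .118, so d = .34. Held to 0.85, the ICC would therefore tolerate an offset of .25 SD and flag one of .5 SD.

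A small example shows the extreme. If one rater scores ten cases 1, 2, 2, 3, 3, 4, 4, 5, 5, 6 and the other gives each case one point more, Spearman is 1.00, exact agreement is 0% and the ICC is .83.

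**2. Yes/no diagnoses.** For two binary ratings Spearman equals phi. If both raters diagnose at the same prevalence p, phi = kappa = 1 − disagreement / (2p(1 − p)).

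| Prevalence | Phi at 90% agreement | Agreement needed for phi of .85 |
|---|---|---|
| 50% | 1 − .10/.50 = .80 | 92.5% |
| 70% | 1 − .10/.42 = .76 | 93.7% |
| 80% | 1 − .10/.32 = .69 | 95.2% |
| 90% | 1 − .10/.18 = .44 | 97.3% |

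A rater exactly at the certification level therefore fails the ongoing standard at every prevalence. Unequal marginals do not rescue this: with all disagreement in one direction and counts of 45, 10, 0 and 45, phi = 2025/2475 = .82.

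**3. Baseline social anxiety disorder.** Entry requires that participants "meet structured interview criteria for SocAD", so the qualifying interview is positive for everyone enrolled. A correlation of that interview with its repeat is undefined, because one variable is constant.

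**4. Precision.** Using Fisher's z with variance (1 + r²/2)/(n − 3), an observed Spearman of .85 has an approximate 95% interval of .64 to .94 with 24 pairs, .73 to .92 with 51 and .76 to .91 with 75. A bare comparison with a cut-off hides this.

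**The case against.** Four points weigh on the other side.

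- **Certification already uses agreement.** A 95% standard on the BPRS and MSIF would be expected to expose a large offset at the start. This stands, so the gap is confined to later drift. The protocol does not say whether agreement means exact or near agreement.
- **There are other ongoing checks.** A reader might infer that drift on the MINI would be missed. The protocol does not support that. The 5% cross-site rating is an agreement-based retraining trigger for diagnostic interviews, and phi above .85 is usually stricter than 90% agreement, so the likelier error is too much retraining. The cross-site check does not clearly extend to the BPRS or MSIF.
- **Effect on the trial's comparisons.** A reader might also infer that rater offset would masquerade as a site difference in Aim 3. Aim 3 tests site as an interaction with condition, and an offset common to both arms at a site largely cancels from that contrast unless evaluators are unevenly spread across arms. Nothing in the protocol suggests they are, and the MINI interviewers are described as blinded. With two evaluators per site, re-interviews would ordinarily pair raters within a site, so even an ICC on these pairs would not reveal a between-site offset.
- **The undefined case is narrow, and kappa does not cure it.** It concerns one diagnosis at one of five time points, and pooled or follow-up pairs can vary. If one rater calls every case positive, kappa is zero whatever the agreement; if both do, it is undefined. This stands and shapes the fix.

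**Conclusion.** The point holds, and it is minor. That Spearman is blind to a constant offset is a mathematical fact; how much it matters depends on offsets the protocol does not give. Over the assumed range of .25 to 1 SD with r = .90, Spearman passes throughout while absolute agreement falls from .87 to .60. The exposure is post-certification drift on the BPRS and MSIF. For MINI diagnoses the fault is a poorly matched and internally inconsistent standard: prevalence-dependent, undefined when a rater never varies, and failed by an evaluator who just met certification.

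It should not be read as a threat to the primary outcomes. The LSAS is listed in Table 4 as subject-reported, and the primary work outcome is the participant's reported paid hours; neither is among the evaluator-rated instruments.

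**What to change.** Keep the 25% re-interviews and change the statistic.

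- **BPRS and MSIF.** Replace Spearman with a two-way random-effects, absolute-agreement, single-rating ICC, keep 0.85 as the criterion, and report the mean difference between raters. Use the same statistics for the comparison with consensus ratings after retraining.
- **MINI diagnoses.** Use percent agreement held to the 90% certification level, with positive and negative agreement, and report kappa where both categories occur.
- **Both.** Give confidence intervals, since one site is expected to supply only about 24 pairs.

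No new data are needed. The cost is that some retraining may be triggered sooner on the rating scales.
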